### 3.3.1. Rationale for Combination Cohorts (C&D)

AML and ALL are highly heterogenous diseases and patients often harbor more than one driver mutation. While recent studies of novel molecularly targeted agents, such as FLT3 inhibitors and IDH1/2 inhibitors, have demonstrated improved response rates and overall survival as monotherapy in patients with relapsed or refractory AML, there is still a high unmet medical need as patients will ultimately succumb to the disease. Combination therapies with molecularly targeted agents have emerged as an attractive strategy to improve efficacy while maintaining a tolerable safety.

The primary objective of the Phase 2 combination Cohorts C & D is to evaluate the safety and tolerability, as well as efficacy, of DS-1594b administered with standard of care backbone regimens. The RP2D will be selected based upon the cumulative safety, efficacy and PK data at the end of the Phase 1 portion, as the anticipated optimal dose considering benefit-risk. Since this will be the first evaluation of DS-1594b administered in combination, both Cohorts C & D will include a safety run-in period (beginning enrollment at one dose level below the RP2D) with pre-specified rules for dose titration under the supervision of the Principal Investigator and the Safety Review Committee, as described in Section 3.3. Additionally, all cohorts will be monitored for toxicity, with pre-specified criteria for early termination if excessive toxicity is predicted, as described in Section 9.3.

## 4. SUBJECT SELECTION

### 4.1. Inclusion Criteria

Each subject must meet **all** the following inclusion criteria to be enrolled in this study.

- a. Provision of written (signed) informed consent form (ICF) by the subject or legal guardian prior to the performance of any study-specific procedures, according to International Council on Harmonisation (ICH) and local regulatory requirements. Subject must be fully informed about their illness and the investigational nature of the study protocol (including foreseeable risks and possible toxicities) and must sign and date an Institutional Review Board (IRB)/Independent Ethics Committee (IEC) approved informed consent form (ICF)(including Health Insurance Portability and Accountability Act authorization [HIPAA], if applicable) before performance of any study-specific procedures or examinations.
- b. Subjects must be willing and able to comply with the protocol.
- c. Subjects with AML or ALL, diagnosed according to the 2016 criteria by the World Health Organization (WHO), who are refractory or relapsed (any salvage) with no available therapies or not candidates for available therapies. For subjects with prior MDS or chronic myelomonocytic leukemia (CMML) or MPN who transformed to AML, therapy received for MDS, CMML, or MPN is NOT considered as prior therapy for AML except for MDS or CMML treated with HMAs. Subjects with MDS or CMML treated with HMA therapies who progress to AML and have no available therapies or are not candidates for available therapies, will be eligible at the time of

progression to AML. In Phase 1: all R/R AML or R/R ALL subjects irrespective of mutations will be eligible. In Phase 2 Cohort A only R/R AML with MLLr will be eligible. In Phase 2 Cohort B only R/R AML with NPM1m will be eligible. In Phase 2 Cohorts C and D: Only R/R AML or R/R ALL subjects with an MLLr or NPM1m will be eligible.

- d. Prior therapy with hydroxyurea, chemotherapy, biological or targeted therapy (e.g. FLT3 inhibitors, other kinase inhibitors), or hematopoietic growth factors is permitted.
- e. Age 18 years or older.
- f. Eastern Cooperative Oncology Group (ECOG) Performance Status 0, 1, or 2.
- g. Adequate hepatic organ function: total bilirubin  $\leq$  1.5 times upper limit of normal (x ULN); aspartate aminotransferase or alanine aminotransferase  $\leq$  2.5 x ULN (aspartate aminotransferase or alanine aminotransferase  $\leq$  5.0 x ULN if deemed related to leukemia by the treating physician)
- h. Creatinine clearance  $\geq$  50 mL/min as calculated using the modified Cockcroft-Gault equation.
- i. Serum electrolytes within the institution's normal limits: potassium, calcium (total calcium, calcium corrected for serum albumin in case of hypoalbuminemia or ionized calcium) and magnesium. If outside of the institution's normal range, subject will be eligible when electrolytes are corrected.
- j. In the absence of rapidly progressive disease, the interval from prior treatment to the time of initiation of protocol therapy will be at least 14 days for prior anti-leukemic therapy with the exception of hydroxyurea as noted below OR at least 5 half-lives for cytotoxic/noncytotoxic agents, whichever is shorter. The half-life for the therapy in question will be based on published pharmacokinetic literature (abstracts, manuscripts, investigator brochure's, or drug-administration manuals) and will be documented in the protocol eligibility document. Since the effect of therapy may be delayed, use of hydroxyurea for subjects with rapidly proliferative disease is allowed before the start of study therapy and on study and hydroxyurea will not require a washout.
- k. Concurrent therapy for CNS prophylaxis or continuation of therapy for controlled CNS disease is permitted. Subjects with a known history of CNS disease or leukemic brain metastasis must have been treated locally, have at least 3 consecutive LPs with no evidence of CNS leukemia, and must be clinically stable for at least 4 weeks prior to enrollment and have no ongoing neurological symptoms that in the opinion of the treating physician are related to the CNS disease (sequelae that are a consequence of the treatment of the CNS disease are acceptable).
- l. Females must be surgically or biologically sterile or postmenopausal (amenorrheic for at least 12 months) or if of childbearing potential, must have a negative serum or urine pregnancy test within 72 hours before the start of the treatment.

m. Women of childbearing potential must agree to use an adequate method of contraception during the study and until 4 months after the last treatment. Males must be surgically or biologically sterile or agree to use an adequate method of contraception during the study until 3 months after the last treatment. In addition, sexually active male subjects must agree to use condoms during the study until 3 months after the last treatment to prevent the potential transmission of the study drug and/or metabolites via semen. Adequate methods of contraception include:

- Total abstinence when this is in line with the preferred and usual lifestyle of the subject. Periodic abstinence (e.g., calendar, ovulation, symptothermal, post-ovulation methods) and withdrawal are not acceptable methods of contraception.
- Female sterilization (have had surgical bilateral oophorectomy with or without hysterectomy) or tubal ligation at least six weeks before taking study treatment. In case of oophorectomy alone, only when the reproductive status of the woman has been confirmed by follow up hormone level assessment
- Male sterilization (at least 6 months prior to screening). For female subjects on the study, the vasectomized male partner should be the sole partner for that subject
- Combination of any of the two following (a+b or a+c or b+c)
  - a. Use of oral, injected or implanted hormonal methods of contraception or other forms of hormonal contraception that have comparable efficacy (failure rate <1%), for example hormone vaginal ring or transdermal hormone contraception. Contraceptives containing ethinyl estradiol should be used with caution (Section 5.6.3).
  - b. Placement of an intrauterine device (IUD) or intrauterine system (IUS).
  - c. Barrier methods of contraception: Condom or Occlusive cap (diaphragm or cervical/vault caps) with spermicidal foam/gel/film/cream/ vaginal suppository.
- In case of use of oral contraception, women should have been stable on the same pill before taking study treatment.
- Note: *Oral contraceptives are allowed but should be used in conjunction with a barrier method of contraception due to unknown effect of drug-drug interaction. Women are considered post-menopausal and not of child-bearing potential if they have had 12 months of natural (spontaneous) amenorrhea with an appropriate clinical profile (e.g. age appropriate, history of vasomotor symptoms) or have had surgical bilateral oophorectomy (with or without hysterectomy) or tubal ligation at least six weeks ago. In the case of oophorectomy alone, only when the reproductive status of the woman has been confirmed by follow up hormone level assessment is she considered not of child-bearing potential.*

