## 3.3. Phase 2 Design

Enrollment in Phase 2 will start once the RP2D has been determined in Phase 1. This Phase 2 study will have four cohorts:

- Cohort A: DS-1594b monotherapy for R/R AML with MLL-r,
- Cohort B: DS-1594b monotherapy for R/R AML with NPM1m,
- Cohort C: DS-1594b in combination with azacitidine and venetoclax for R/R AML with NPM1m or MLLr
- Cohort D: DS-1594b in combination of mini-HCVD for R/R ALL with MLLr

Subjects enrolled in Cohorts A and B will receive the RP2D dose of DS-1594b determined in Phase 1. Cohorts C and D will enroll an initial 6 subjects in a safety run-in at one dose level below the RP2D (Dose level 0) with DS-1594b dose titration as specified below.

Cohorts A and B (single agent cohorts) will enroll a maximum of 26 subjects, and Cohorts C and D (combination cohorts) will enroll a maximum of 32 subjects, to allow reasonable determination of CRc within 3 months of therapy initiation.

For the combination cohorts (C & D) there will be a safety-run in evaluation with pre-defined toxicity stopping rules to be implemented for early DLT evaluation as per following plan:

- Safety run-in evaluation by the Safety Review Committee of the first 6 subjects in cohorts C and D will occur after 6 subjects have completed at least one cycle of treatment (or at least 28 days from the first day of treatment).
- Enrollment will be paused while the first 6 subjects are evaluated for safety. Each combination cohort will be evaluated independently.
  - If  $\leq 1$  of the 6 subjects experiences DLT in the first cycle of treatment, the treatment combination will be considered as safe and the DS-1594b dose can be escalated to the RP2D (Dose level 1) for the treatment of the next 6 patients (repeat the safety run-in evaluation). If the RP2D (Dose level 1) is considered safe, continue enrollment of an additional 20 subjects at the RP2D (i.e. total subjects treated at the RP2D will be 26 subjects; total cohort size will be 32 subjects). If  $\geq 2$  of 6 subjects at the RP2D experiences DLT in the first cycle of treatment, de-escalate and continue enrollment of an additional 20 subjects at Dose Level 0.

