### **9.2. Phase 2**

The primary endpoint of cohorts A-C is the achievement of CR + CRh within 3 months of therapy initiation in subjects with R/R AML with MLLr or NPM1m. The primary endpoint of cohort D is the achievement of CR + CRI within 3 months of therapy initiation in subjects with R/R ALL with MLLr. Up to 26 subjects will be enrolled per cohort in Cohorts A and B and up to 32 subjects will be enrolled per cohort in Cohorts C and D. Each cohort will be analyzed separately. Treatment will be considered encouraging if the CR/CRh rate (Cohorts A, B, and C) or CR/CRI rate (Cohort D) rate would reach at least 40%, an improvement over the historical rate by more than 15%. The study will monitor futility and toxicity using the Bayesian method of Thall, Simon and Estey.

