## 9.4. Statistical Analysis Plan

### 9.4.1. Analysis Sets

#### 9.4.1.1. Efficacy Analysis Set

The efficacy analysis set is all subjects with MLLr or NPM1m who received at least one dose of DS-1594b. Each cohort will be analyzed separately for efficacy.

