**Table 33: Phase 2 Cohorts A & B Schedule of Events**

Phase 2 Cohorts A & B																				
Procedure	SCR		C1						C2		C3		C4		Cx		EOT	30D FU	LT FU	Comment
Day	-14	1	2	8	9	15	28	1	28	1	28	1	28	1	28					
Window			$\pm 1D$	$\pm 1D$	$\pm 1D$	$\pm 1D$	$\pm 4D$	$\pm 3D$	$+7D$	$\pm 14D$										
Informed Consent	X																		Prior to study procedures	
Bone Marrow Aspirate/Biopsy	X						X		X		X					X*	X		* Day 28 ( $\pm 4$ ) of Cycles 1, 2, 3, 6, 9, and EOT	
Confirm NPM1-m or MLL-r	X																			
Eligibility Assessment	X																			
Demographics, Medical & Disease History	X																		WHO classification, cytogenetics, mutations, prior therapy	
Vital Signs	X	X		X		X		X		X		X		X		X			Blood pressure, pulse rate, respiratory rate, and temperature taken $\sim 5$ min prior to ECG measurements	
ECG (in triplicate) by 12-lead or Holter	X	X		X		X		X		X		X		X*		X			* Cycles 5 and 6 only. Triplicate ECGs $\geq 1$ minute apart, supine/semi-recumbent. Prior to PK. See Section 8.5 and Table 21 Table 24 for timing of ECGs.	
Height	X																		Screening procedures should be done 3 days before C1D1.	
Weight	X	X					X		X		X		X		X					
BSA	X																		Calculate by Mosteller formula	
SpO2	X	X					X		X		X		X		X					
Physical Exam	X	X					X		X		X		X		X					

Formatted: C-Hyperlink, Font: 8 pt

Phase 2 Cohorts A & B																								
Procedure	SCR	C1						C2		C3		C4		Cx		EOT	30D FU	LT FU	Comment					
Day	-14	1	2	8	9	15	28	1	28	1	28	1	28	1	28									
Window			±1D	±1D	±1D	±1D	±4D	±4D	±4D	±4D	±4D	±4D	±4D	±4D	±4D	±3D	+7D	±14D						
ECOG PS	X	X						X		X		X		X		X								
ECHO/MUGA	X																	≤30 days prior to first dose						
SAEs	X	Continuously																						
AEs		Continuously																						
Prior Medications, Non-Drug Therapies, and Radiotherapy	X																							
Concomitant Medications, Non-Drug Therapies, and Radiotherapy	X	Continuously																						
Hematology, Coagulation, Chemistry	X	X	≥ 3 times weekly			≥ 2 times weekly			1-2 times weekly			X						Screening procedures should be done 3 days before C1D1. CBC with Differential, PLT, Serum Creatinine, Electrolytes, Glucose, Uric acid, calcium, magnesium, BUN After C6, less frequent at guidance of PI						
Hepatic Labs	X	X	≥ 3 times weekly			≥ 2 times weekly			1-2 times weekly			X						AST, ALT, Alk phos, Total Bilirubin (fractionated)						

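### Inclusion criterion 4.1c pools Cohorts C and D under one rule that contradicts their stated populations; even on a lenient reading it lets NPM1m ALL without MLLr into Cohort D

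*Combined protocol and SAP*

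**What the plan says.** Section 4.1 requires every listed inclusion criterion to be met before enrolment. Criterion c gives the monotherapy cohorts one rule each: "In Phase 2 Cohort A only R/R AML with MLLr will be eligible" and "In Phase 2 Cohort B only R/R AML with NPM1m will be eligible". It then covers the two combination cohorts together: "In Phase 2 Cohorts C and D: Only R/R AML or R/R ALL subjects with an MLLr or NPM1m will be eligible".

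The design text keeps those two cohorts apart. Section 3.3 has "Cohort C: DS-1594b in combination with azacitidine and venetoclax for R/R AML with NPM1m or MLLr" and "Cohort D: DS-1594b in combination of mini-HCVD for R/R ALL with MLLr". The Section 3 overview and the objectives column of Table 1 agree with it. Section 9.2 states the Cohort D primary endpoint, CR+CRi within 3 months, "in subjects with R/R ALL with MLLr", and ties the Cohort A to C endpoint, CR+CRh, to R/R AML with either marker.

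Section 9.4.1.1 defines one Efficacy Analysis Set: "all subjects with MLLr or NPM1m who received at least one dose of DS-1594b". It adds that cohorts are analyzed separately. The schedules for Cohorts A and B (Table 33) and Cohort C (Table 34) carry a screening row "Confirm NPM1-m or MLL-r"; the Cohort D schedule (Table 35) has none.

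**The concern.** Criterion 4.1c is the text a site applies at screening, and for Cohorts C and D it is wider than the populations the objectives and endpoints refer to. A subject can satisfy it and still fall outside the cohort as defined in Section 3.3.

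Each combination cohort is a single arm with its own futility rule and its own response estimate. If the entry rule is wider than the stated population, the estimate may describe a mixture that the objective does not name. This matters most for Cohort D, where the excess is one of marker and not only of lineage, and where nothing later in the analysis plan removes the subject.

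**Working it through.** **Step 1: the plan's own figures.** These were checked first, to see whether the eligibility wording touches them.

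- Futility rule (Section 9.3): stop if Pr(P_E ≤ 0.40 | data) > 0.95, with a beta(0.5, 0.5) prior. The largest stopping counts are 1 of 10, 2 of 15, 4 of 20 and 6 of 26, as in Table 22.
- Exact binomial recursion over looks at 10, 15 and 20, with a maximum of 26, at true rates 0.1 to 0.6: early-stop probabilities 0.9633, 0.6713, 0.2906, 0.0811, 0.0153 and 0.002, as in Table 23.
- 95% credible interval for 11 of 26: beta(0.5 + 11, 0.5 + 15) = beta(11.5, 15.5), giving 24.96% to 61.27%. The plan states 25% to 61.3%.
- Total enrolment: 66 + 2 × 26 + 2 × 32 = 182, as stated.

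None of these uses the eligibility wording as an input, so all stand.

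**Step 2: who passes.** Two lineages and two markers give four combinations. NPM1m here means without MLLr.

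| Combination | Section 3.3: C | Section 3.3: D | 4.1c read literally: C and D | 4.1c with lineage fixed: C | 4.1c with lineage fixed: D |
|---|---|---|---|---|---|
| AML, MLLr | yes | no | yes | yes | no |
| AML, NPM1m | yes | no | yes | yes | no |
| ALL, MLLr | no | yes | yes | no | yes |
| ALL, NPM1m | no | no | yes | no | **yes** |

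Read literally, 4.1c admits all four to each cohort, against two intended for C and one for D. With lineage fixed (AML to C, ALL to D), Cohort C matches its definition exactly. Cohort D admits two combinations where one is intended; the excess is NPM1m ALL.

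**Step 3: does later text remove that subject from Cohort D?**

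- Section 9 and the Section 5.5 heading describe Cohort D by lineage only, so they do not settle the marker.
- Section 8.9.3 lists enrolment criteria as a class of deviation, but this subject meets 4.1c as written. A monitor could object only by preferring Section 3.3 over Section 4.1.
- Section 8.2 requires the tests to be done. It does not say which result qualifies for which cohort.
- Table 35 has a general eligibility row, which refers back to the Section 4 criteria, and no marker row.
- The Efficacy Analysis Set accepts either marker in either lineage, so the subject remains in it.

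No step excludes the subject. A Cohort D subject with NPM1m ALL would enter the CR+CRi numerator or denominator and, once past the run-in, the futility count.

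**The case against.** The strongest reply is that the intent is clear. Section 3.3, Table 1, Section 3 and Section 9.2 agree on both populations; Section 9 and the headings of Sections 5.4 and 5.5 fix lineage again. Section 2.3 describes NPM1 mutation only in AML, and Section 7.1 ties the NPM1 indication to AML. On that view 4.1c is loose drafting that no site would act on. Most of this stands for lineage: placing AML in Cohort D or ALL in Cohort C would contradict several sections at once and is unlikely. It does not close the marker gap, because 4.1c names NPM1m as qualifying and is the operative rule.

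A reader might also draw stronger conclusions that the documents do not support:

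- *That a misplaced subject would be scored by the other leukemia's criteria.* Sections 8.8.1 and 8.8.2 set response criteria by disease and define CR, CRh and CRi for both. The mismatch is in the population, not the scoring.
- *That each misplaced subject costs 1/26 = 3.8 percentage points, or could decide the look that stops at 0 or 1 of 10.* Both are true of any subject in a cohort of 26. They give the weight of one observation, not an expected bias.
- *That futility stopping is materially inflated.* If 10% to 30% of a cohort were outside the population and responded at 10% to 25%, with the rest at 40%, the stop probability would rise from 0.081 to between 0.101 and 0.261. Both the shares and the response rates are assumptions; nothing in the documents suggests contamination of that order.
- *That Cohort D goes untested for the marker because Table 35 lacks the row.* Section 8.2 already requires the test, and the row in Table 33 is itself shared by two cohorts with different markers.

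**Conclusion.** The contradiction is real and follows from the text alone. Criterion 4.1c is wider than the stated populations of both combination cohorts when read literally. On the most lenient reading it is still wider for Cohort D, by one combination: ALL with NPM1m and no MLLr. Such a subject would be validly enrolled under 4.1c and retained in the Efficacy Analysis Set, so Cohort D's primary rate and futility count could include people its endpoint is not stated for.

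The size cannot be estimated, since the documents give no frequency for NPM1m ALL, and the practical effect may be small. The inference that the design figures are wrong is not supported: sample sizes, boundaries, stopping probabilities and intervals reproduce and do not depend on this sentence.

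The conclusion assumes that Section 3.3, with which Table 1's objectives and Sections 3 and 9.2 agree, states the intended populations. It should be corrected because an eligibility rule is wrong as written and the correction is nearly free.

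**What to change.** Split the last sentence of 4.1c into two that repeat Section 3.3, in the form already used for Cohorts A and B: Cohort C, only R/R AML with MLLr or NPM1m; Cohort D, only R/R ALL with MLLr.

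For consistency with Tables 33 and 34, add a screening row 'Confirm MLL-r' to Table 35.

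Redefining the Efficacy Analysis Set by cohort-specific disease and marker is optional once 4.1c is corrected. The set is not limited to Phase 2, cohorts are already analyzed separately, and Section 9.4.6 repeats the efficacy analyses in the Safety Analysis Set, where a wrongly enrolled subject would remain in any case.

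The cost is amendment wording in one criterion and one table row. No test, visit, sample size or boundary changes.

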#### 4.2. **Exclusion Criteria**

- a. Subjects with a known allergy, hypersensitivity, or contraindication to the protocol therapies or any of their components to be used in the arm the subject is to be enrolled on.
- b. Uncontrolled or significant cardiovascular disease, including any of the following:
  - Bradycardia of less than 50 beats per minute, unless the subject has a pacemaker;
  - QTcF interval >450 msec;
  - Diagnosis of or suspicion of long QT syndrome (including family history of long QT syndrome);
  - Systolic blood pressure  $\geq$ 180 mmHg or diastolic blood pressure  $\geq$ 110 mmHg;
  - History of clinically relevant ventricular arrhythmias within 6 months prior to screening (eg, ventricular tachycardia, ventricular fibrillation, or Torsade de Pointes);
  - History of second (Mobitz II) or third-degree heart block (subjects with pacemakers are eligible if they have no history of fainting or clinically relevant arrhythmias while using the pacemaker);
  - History of uncontrolled angina pectoris, unstable angina or myocardial infarction, CABG, CVA, TIA, symptomatic pulmonary emboli within 6 months prior to Screening;
  - New York Heart Association Class 3 or 4 heart failure;
  - Left ventricular ejection fraction (LVEF)  $\leq$ 50 or less than the institutional lower limit of normal;
  - Complete left bundle branch block (right bundle branch block is permitted, but requires manual reading of the QTc interval);
  - Active cardiac dysrhythmias of NCI CTCAE grade  $\geq$  2 (eg, atrial fibrillation).
- c. Persisting toxicity related to prior therapy of Grade  $>$ 1 NCI-CTCAE v 5.0; however, alopecia and sensory neuropathy Grade 2 or lower is acceptable
- d. Underwent HSCT within 90 days of the first dose of protocol therapy, or subjects with clinically significant (Grade 2 or greater) graft-versus-host disease (GVHD) (the use of topical steroids for ongoing cutaneous GVHD is permitted)
- e. Subjects with symptomatic CNS leukemia or subjects with poorly controlled CNS leukemia.
- f. Active and uncontrolled disease (active infection requiring systemic therapy, fever likely secondary to infection within prior 48 hours, uncontrolled hypertension despite adequate medical therapy as judged by the treating physician).
- g. Active (uncontrolled, metastatic) other malignancies
- h. Major surgery within 28 days prior to the first dose of protocol therapy

- i. Known dysphagia, short-gut syndrome, gastroparesis, or other conditions that limit the ingestion or gastrointestinal absorption of drugs administered orally
- j. Known history of testing positive for HIV or known acquired immunodeficiency syndrome (test at screening only if required by local regulations)
- k. Known history of Hepatitis B virus (HBV) or hepatitis C virus (HCV) infection with active Hepatitis B or C infection at screening (positive HBV surface antigen or HCV RNA if anti-HCV antibody screening test positive)
- l. Vaccination with live-attenuated vaccines within 4 weeks of the first dose of study drug and while on trials is prohibited (COVID-19 vaccination is permitted)
- m. Subjects who are currently receiving treatment with medication that meet one of the following criteria and that cannot be discontinued at least one week prior to the start of DS-1594b treatment:
  - Medications that may prolong QTc interval and have a known risk of inducing Torsades de Pointes unless it is vital for the care of the subjects (see Appendix [Table 28](#)[Table 29](#))
  - Strong inhibitors or inducers of CYP3A (see Appendix [Table 29](#)[Table 29](#))
  - CYP3A and CYP2C19 substrates with narrow therapeutic index (see Appendix [Table 29](#)[Table 29](#))
- n. Subjects who consume grapefruit products, Seville oranges, or Star fruit within 3 days prior to the first DS-1594b administration and until the last day of DS-1594b is completed.
- o. **Additional exclusion criteria for the DDI sub-study and food effect sub-study (see Appendix [Table 31](#)[Table 34](#))**
  - Subjects who are currently receiving moderate inhibitors or inducers of CYP3A who cannot discontinue at least one week prior to the start of DS-1594b treatment till the end of sub-study period (note that strong CYP3A inhibitors or inducers still need to be restricted as defined in Section [4.2m](#)).
  - Subjects who are currently receiving proton pump inhibitors who cannot discontinue at least 2 days prior to the start of DS-1594b treatment till the end of sub-study period.
- p. Other severe acute or chronic medical conditions that is active and not well controlled including renal, skeletal muscle, adrenal insufficiency, colitis, inflammatory bowel disease, or psychiatric conditions including recent (within the past year) or active suicidal ideation or behavior; or laboratory abnormalities that may increase the risk associated with study participation or study treatment administration or may interfere with the interpretation of study results and, in the judgment of the investigator, would make the subject inappropriate for entry into this study.
- q. Subjects unwilling or unable to comply with the protocol, including:
  - Pregnant or breastfeeding women or women of childbearing potential who are unable to comply with appropriate contraception as outlined in Section [4.1m](#) or

who plan to become pregnant while in the study or for at least 6-7 months after last administration of study treatment

- Known alcohol or drug abuse within the last 1 year
- In a man whose sexual partner is a woman of childbearing potential, unwillingness or inability to use an acceptable contraceptive method for the entire study period and for at least 3 months after study completion
- r. Acute promyelocytic leukemia (APL).
- s. Uncontrolled or poorly controlled adrenal or pituitary disease (including adrenal insufficiency, Addison's disease, Cushing's disease)

